
N
	
A sufficient number of subjects will be screened to randomize 600 subjects in a 3:3:2 ratio (225 in each lofexidine group and 150 in the placebo group) at approximately 12 study sites in the US. The total number of subjects randomized at each site will depend on subject availability and will likely not be evenly distributed at all sites.

Primary Endpoint	
Days 1-7: Randomized, Double-Blind, Placebo-Controlled Treatment
 
 
• Area under the curve (AUC) based on Short Opiate Withdrawal Scale of Gossop (SOWS-Gossop) scores from Days 1 through 7.
 

Secondary Endpoint	
Days 1-7: Randomized, Double-Blind, Placebo-Controlled Treatment
 
 
• Completion status (whether a subject receives at least one dose of study medication on Day 7 and completes the 3.5-hour post-dose SOWS-Gossop assessment on Day 7).
 

Tertiary/ Exploratory Endpoints	
Days 1-7: Randomized, Double-Blind, Placebo-Controlled Treatment
 
 
• SOWS-Gossop, OOWS-Handelsman, Modified Clinical Global Impression (MCGI [Subject and Rater]), Visual Analog Scale for Efficacy (VAS-E), and Clinical Opiate Withdrawal Scale (COWS) scores on Days 1, 2, 3, 4, 5, 6, and 7;
 
• Retention analysis (time to removal from study treatment) over the 7 inpatient days;
 
• Status of detoxification on Day 7 or early termination as assessed by the Site Investigator;
 
• Concomitant medication analysis;
 
• Withdrawal-related adverse event analysis;
 
• Evaluation of subject treatment status 30 days after last dose; and
 
• In addition, single items (e.g., sweating, anxiety) from the OOWS-Handelsman and COWS that are not included in the SOWS-Gossop may be analyzed, as may AUC based on COWS scores from Days 1 through 7.
 
 
Days 8-14: Open-Label, Continuation Treatment
 
 
• Descriptive evaluation of SOWS-Gossop, OOWS-Handelsman, MCGI (Subject and Rater), VAS-E, and COWS;
 
• Duration of exposure;
 
• Number/proportion of subjects successfully completing detoxification as assessed by the Site Investigator;
 
• Distribution of number of days required to complete detoxification as assessed by the Site Investigator;
 
• Average daily dose of lofexidine; and
 
• Concomitant medications.
 

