#### **15.4.8 Withdrawal-Related Adverse Events**

The Site Investigator will indicate, using his/her best judgment, whether any adverse event that occurs during the study is secondary to opioid withdrawal. Individual items reported on the efficacy scales (i.e., SOWS-Gossop, OOWS-Handelsman) do not automatically qualify as a withdrawal-related AE unless the subject specifically reports them in response to a non-leading question (i.e., “How have you been feeling since I saw you last?”). In the event a subject reports “withdrawal” or a similar event encompassing a collection of potential withdrawal symptoms, the subject should be asked to elaborate so that specific symptoms can be recorded on the AE eCRF. In this case, the AEs recorded should include both the original reported condition (e.g., “withdrawal syndrome”) as well as the individual symptoms that the subject lists after further inquiry (e.g., anxiety, upset stomach).

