### **16.7 Adverse Event Reporting**

In accordance with FDA reporting requirements, all AEs occurring during the course of the clinical trial will be collected, documented, and reported by the Site Investigator or sub-investigators according to the specific instructions detailed in this section of the protocol and [Appendix 6](#). The occurrence of AEs will be assessed starting at the treatment phase of the protocol.

An AE is defined as any reaction, side effect, or untoward event that occurs during the course of the clinical trial, whether or not the event is considered related to the investigational agent or clinically significant. For this study, events reported by the subject, as well as clinically significant abnormal findings in the opinion of the Investigator on physical examination, laboratory evaluation, or C-SSRS (for example, score of 3 or more on the scale) will be considered an AE and will be recorded in the subject's source document and on the AE eCRF. A new illness, symptom, sign or clinically significant clinical laboratory abnormality or worsening of a pre-existing condition or abnormality is considered an AE. Stable chronic conditions, such as arthritis, which are present before clinical trial entry and do not worsen are not considered AEs.

After each AE assessment, the physician will record in the subject's source document and on the AE eCRF the type of AE and whether serious (SAE) or non-serious, severity of each AE, and the relationship to the study agent. These categories are asking for the physician's best judgment of the severity and relatedness of each AE. The physician will also record, based on his/her best judgment, whether the AE is secondary to opioid withdrawal (see [Section 15.4.8](#)). In general, an AE should not be marked as withdrawal related AND related to study medication.

Each day, a study physician must review any AEs that are reported as beginning or as continuing. All AEs, including clinically significant abnormal findings on laboratory evaluations, regardless of severity, will be followed by a study physician until satisfactory resolution.

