### 17.2.11 Safety Measures

The safety measures during Days 1-7 of the study are AEs, vital signs, ECGs (primarily evaluated for changes in QTcF versus time-matched controls for both doses of lofexidine and placebo), clinical laboratory measures, physical exams, and suicidal ideation and behavior. Adverse event summaries will include tabulations overall and by seriousness, severity, and causality assessment. The data from these measures recorded during Days 1-7 will be summarized descriptively by treatment group. In addition, each lofexidine group will be compared inferentially to the placebo group using chi-square tests for categorical variables and t-tests within an analysis of variance for continuous variables; the resulting p-values will not be adjusted for multiple testing.

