2. SAMPLE SIZE

Treatment effect and subject variability with respect to SOWS-Gossop scores were estimated from the prior Phase 3 study (USWM-LX1-3002), using the random coefficients model planned for the present study and estimating the treatment effect of 3.2 mg lofexidine versus placebo with respect to area under the curve (AUC) based on the SOWS-Gossop scores from Days 1 through 7 (AUC(1-7)). It was assumed that the treatment effect of the 2.4 mg lofexidine dose will be three-fourths the treatment effect of the 3.2 mg dose. The table below shows the power to find a significant treatment effect for the comparisons of the two lofexidine treatments versus placebo, assuming a sample size allocation ratio of 3:3:2 (3.2 mg lofexidine : 2.4 mg lofexidine : placebo) and accounting for the sequential testing approach described in Section 6.1. The power to find a statistically significant effect of the 3.2 mg lofexidine dose with respect to AUC (1-7) is in excess of 90% with the planned total sample size of 600.

	Power (%) with Respect to AUC (1-7)		
Total Sample Size	3.2 mg Lofexidine versus Placebo	2.4 mg Lofexidine versus Placebo	
600	94.6	72.6	
550	92.6	67.6	
500	90.1	62.2	
450	86.8	55.7	

Effective: 14-Feb-13

Page 4 of 26

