All AEs will be listed and tabulated by severity, relationship to study medication, primary system organ class and preferred term according to MedDRA Version 16.0. In counting the number of events reported, a continuous event, i.e., an event reported more than once and which did not cease, will be counted only once with the worst recorded severity; non-continuous AEs reported several times by the same subject will be counted as multiple events. Events present immediately prior to the first dose of study medication that do not worsen in severity, will not be regarded as treatment emergent. Events with start dates more than 30 days after the administration of the last dose of study medication will not be considered treatment emergent and will be listed separately. In deriving the tabulation relating to preferred term reporting, the severity of a recurrent AE will be taken to be the most severe and the relationship to study medication as the highest probable.

The following will be summarized and presented for the overall population and by treatment group:

- The number and percentage of subjects experiencing at least 1 treatment emergent TEAE by MedDRA preferred term and SOC. A chi-squared test will be used to test for a difference in the percentage of subjects experiencing at least 1 TEAE between each of the 2 Lofexidine doses and placebo.
- The number and percentage of subjects experiencing an opioid withdrawal related TEAE by MedDRA preferred term and SOC.
- The number and percentage of subjects experiencing TEAEs by severity of event
- The number and percentage of subjects experiencing TEAEs by relationship to IP
- The number and percentage of subjects experiencing treatment-related adverse events (i.e. Possibly Related, Probably Related, Definitely Related)
- The number and percentage of subjects experiencing at least 1 treatment emergent SAE by MedDRA preferred term and SOC
- The number and percentage of subjects experiencing SAEs by severity of the event
- The number and percentage of subjects experiencing SAEs by relatedness to IP

Adverse events whilst receiving Lofexidine therapy during the open-label phase

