6.14 Change to Planned Protocol Analysis

The following changes have been made to the planned protocol analyses sections:

Section 17.2.7 Control of the False Positive Rate and Statistical Testing Strategy

Change: All statistical tests will be two-sided at the 0.05 significance level. This is a change from the protocol, where it was specified that statistical tests would be one-sided at the 0.025 significance level.

Reason: Two-sided statistical tests at the 0.05 significance level is statistical convention for hypothesis testing.

Section 17.2.8.1 SOWS-Gossop AUC (1-7)

Change: A number of sensitivity analyses have been added and are detailed in section 16.9.2 of the statistical analysis plan.

Reason: To provide additional sensitivity analyses of log_e (SOWS-Gossop score +1) from day 1 to day 7 under differing mechanisms for missing data, including Missing at Random (MAR) and Missing Not at Random (MNAR)

Section 17.2.8.2 Completion Status

Change: A logistic regression model including fixed effects for treatment group, gender and site will be used instead of a Cochran-Mantel Haenszel test to test for a difference in completion status between the 2 Lofexidine groups and placebo.

Reason: To additionally adjust for site in the analysis and to provide an interpretation of the effect of treatment using odds ratios.

Sections: 17.2.8.3 SOWS-Gossop on Days 1, 2, 3, 5, 6 and 7 and 17.2.8.4 OOWS-Handelsman, MCGI (Subject and Rater), VAS-E, and COWS

Change: A MMRM model will be used to test for a difference in the log_e (SOWS-Gossop score +1) at each of days 1 through 7 between the 2 Lofexidine groups and placebo. This replaces planned pattern-mixture approach used in the principal analysis.

Reason: MMRM model is a standard approach for the analysis of treatment differences at different time points when there are repeated measures.

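### The one adverse-event test named in SAP 6.13 is on any TEAE, which pools withdrawal symptoms with drug effects and can mask a drug-type excess if withdrawal TEAEs are common

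*SAP*

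**What the plan says.** **The test.** SAP 6.13, on adverse events during the double-blind phase, lists the summaries to be produced. The first bullet covers subjects with at least one TEAE by MedDRA preferred term and SOC, and adds: "A chi-squared test will be used to test for a difference in the percentage of subjects experiencing at least 1 TEAE between each" of the two doses and placebo. No other bullet in that list names a test. Neither SAP addendum changes it.

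**The protocol's plan.** Protocol 17.2.11 is wider. For the safety measures generally, "each lofexidine group will be compared inferentially to the placebo group using chi-square tests for categorical variables", with p-values not adjusted for multiplicity. SAP 6.14, which lists departures from the protocol, does not mention safety testing.

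**What counts as an AE.** Protocol 15.4.8 brings withdrawal symptoms in when the subject reports them: "the subject should be asked to elaborate so that specific symptoms can be recorded on the AE eCRF", and "the AEs recorded should include both the original reported condition" as well as the individual symptoms. Protocol 16.7 adds: "The occurrence of AEs will be assessed starting at the treatment phase of the protocol". SAP 6.13 excludes events present just before the first dose that do not worsen, but nothing removes withdrawal symptoms as such from the TEAE count.

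**What is already separated.** Protocol 15.5.1 and 16.7 have the physician record whether each AE is secondary to opioid withdrawal, and say that an AE should in general not carry both that mark and a drug-related one. SAP 6.13 tabulates by arm, without a test, withdrawal-related TEAEs, TEAEs by severity and by relationship, treatment-related AEs, and SAEs. SAP 6.1 asks for 95% confidence intervals on treatment comparisons.

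**The concern.** Subjects are in abrupt opioid withdrawal and are asked every day how they have been feeling. The trial's hypothesis is that lofexidine relieves withdrawal symptoms. The dose-hold and discontinuation rules show that lowered blood pressure and heart rate are the drug effects being watched.

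A single yes/no on any TEAE puts both kinds of event into one count. Two things can then hide a drug-type excess:

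- **Dilution.** A subject who already counts because of a withdrawal TEAE cannot count again because of a drug effect.
- **Offset.** If lofexidine lowers withdrawal TEAEs, that fall is subtracted from the rise in drug effects.

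The interval required by SAP 6.1 does not help, because it attaches to the same mixed percentage. At stake is whether the one named inferential AE result bears on tolerability at each dose.

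**Working it through.** **Inputs from the documents**

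- Arm sizes: Protocol synopsis, "randomize 600 subjects in a 3:3:2 ratio (225 in each lofexidine group and 150 in the placebo group"). Check: 600 × 3/8 = 225 and 600 × 2/8 = 150. The SAP sample-size section uses the same 3:3:2 split. Each comparison is 225 versus 150.
- Level: SAP 6.14, "All statistical tests will be two-sided at the 0.05 significance level".
- The plan states no power, TEAE rate or detectable difference for the AE test, so there is no stated figure to reproduce beyond the split.

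**Assumptions**

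- All randomized subjects are dosed.
- Drug-type AEs occur in 10% on placebo and 25% on lofexidine.
- Withdrawal TEAEs and drug-type AEs are independent within a subject.
- The chi-squared test has no continuity correction. Power is by exact binomial enumeration and counts only significant results in the direction of more events on lofexidine.

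**Formula.** With withdrawal-TEAE rate w and drug-type rate d, any-TEAE = 1 − (1 − w)(1 − d). If w is the same in both arms, the difference in any-TEAE is (1 − w) × (0.25 − 0.10), so the 15-point excess shrinks by the factor 1 − w.

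| Withdrawal TEAEs, both arms | Any-TEAE placebo | Any-TEAE lofexidine | Difference (points) | Power |
|---|---|---|---|---|
| Drug-type events tested alone | 10% | 25% | 15 | 97% |
| 10% | 19% | 32.5% | 13.5 | 84% |
| 20% | 28% | 40% | 12 | 67% |
| 50% | 55% | 62.5% | 7.5 | 31% |
| 80% | 82% | 85% | 3 | 12% |
| 90% | 91% | 92.5% | 1.5 | 8% |

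Worked row: at w = 50%, placebo is 1 − 0.5 × 0.90 = 55%, lofexidine is 1 − 0.5 × 0.75 = 62.5%, and the difference is 0.5 × 15 = 7.5 points.

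**A larger assumed excess.** With drug-type events at 20% versus 40%, power is 99% alone, then 95%, 87%, 52%, 20% and 11% at the same five withdrawal rates.

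**If lofexidine also lowers withdrawal TEAEs.** Suppose they fall from 90% to 81%, with drug-type events again 10% versus 25%. Any-TEAE is 1 − 0.10 × 0.90 = 91% on placebo and 1 − 0.19 × 0.75 = 85.75% on lofexidine. The test is then significant in lofexidine's favour 32% of the time and shows an excess 0.02% of the time. Exact offset needs less: from 80% on placebo, 1 − w must equal 0.20 × 0.90 / 0.75 = 0.24, a fall to 76%.

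**The case against.** **The test may be per term.** The sentence sits in a bullet about preferred terms and SOCs, and Protocol 17.2.11 speaks of chi-square tests for categorical variables generally. If each term is tested, hypotension and bradycardia are compared on their own and nothing is pooled. This stands as an ambiguity: a reader might infer that any-TEAE is the only AE test, but the documents do not settle it.

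**The separate information exists.** The treatment-related row is already close to a drug-type endpoint, because an AE is generally not marked both ways. Blood pressure has threshold tables, and ECGs have their own report. An excess of 10% versus 25% would show in the printed counts. This stands too: what is missing is a test and an interval on that row, not the data.

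**The rates are chosen.** Protocol 15.4.8 says scale items do not automatically qualify as withdrawal-related AEs, and SAP 6.13 drops unchanged pre-dose events. With withdrawal TEAEs at 10% to 20%, much or most of the power remains. This also stands. In reply, AE recording starts only at treatment, which makes the pre-dose rule harder to apply. High rates are plausible in abrupt withdrawal, but they are assumed.

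**Nobody proposes to read non-significance as safety.** A reader might infer that a null p-value will be taken as good tolerability. No section says so, and the stated safety hypothesis is a descriptive comparison of the two doses.

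**Conclusion.** The point holds as a conditional one. Read as an overall test, the named AE comparison can mask a drug-type excess if withdrawal TEAEs are common. For 10% versus 25%, power falls from 97% alone to 31% at a withdrawal-TEAE rate of 50% and 8% at 90%. It is still 84% at 10% and 67% at 20%. These figures rest on assumed rates and on independence within subjects.

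Two stronger readings are not supported. A reader might say that the excess will be missed at this sample size. But the same 150 versus 225 subjects detect it 97% of the time when it is tested alone, so the composite is the cause. A reader might also say that the two effects cancel. That needs lofexidine to lower withdrawal TEAEs by enough; with equal rates the mechanism is dilution.

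It is a worthwhile and inexpensive improvement to the safety analysis, and it leaves the efficacy analysis untouched.

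**What to change.** In SAP 6.13, for each dose versus placebo:

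1. Report the risk difference with its 95% CI, and the chi-squared test, for subjects with at least one TEAE not marked as secondary to opioid withdrawal.
2. Report the same, separately, for withdrawal-related TEAEs.
3. Keep any-TEAE as a descriptive row.
4. State whether the tests are overall or per preferred term/SOC, and reconcile this with Protocol 17.2.11. If the SAP is meant to be narrower, list that in SAP 6.14.

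The cost is SAP wording and two table rows, from a mark already on the AE eCRF. The downside is that the withdrawal mark is a blinded investigator judgement with some misclassification, which is the reason to keep the any-TEAE row beside the new ones.

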6.14 Change to Planned Protocol Analysis

The following changes have been made to the planned protocol analyses sections:

Section 17.2.7 Control of the False Positive Rate and Statistical Testing Strategy

Change: All statistical tests will be two-sided at the 0.05 significance level. This is a change from the protocol, where it was specified that statistical tests would be one-sided at the 0.025 significance level.

Reason: Two-sided statistical tests at the 0.05 significance level is statistical convention for hypothesis testing.

Section 17.2.8.1 SOWS-Gossop AUC (1-7)

Change: A number of sensitivity analyses have been added and are detailed in section 16.9.2 of the statistical analysis plan.

Reason: To provide additional sensitivity analyses of log_e (SOWS-Gossop score +1) from day 1 to day 7 under differing mechanisms for missing data, including Missing at Random (MAR) and Missing Not at Random (MNAR)

Section 17.2.8.2 Completion Status

Change: A logistic regression model including fixed effects for treatment group, gender and site will be used instead of a Cochran-Mantel Haenszel test to test for a difference in completion status between the 2 Lofexidine groups and placebo.

Reason: To additionally adjust for site in the analysis and to provide an interpretation of the effect of treatment using odds ratios.

Sections: 17.2.8.3 SOWS-Gossop on Days 1, 2, 3, 5, 6 and 7 and 17.2.8.4 OOWS-Handelsman, MCGI (Subject and Rater), VAS-E, and COWS

Change: A MMRM model will be used to test for a difference in the log_e (SOWS-Gossop score +1) at each of days 1 through 7 between the 2 Lofexidine groups and placebo. This replaces planned pattern-mixture approach used in the principal analysis.

Reason: MMRM model is a standard approach for the analysis of treatment differences at different time points when there are repeated measures.

17.2.8.5 Retention Analysis (Time to Removal from Study Treatment)

Change: Gender will be included in the Cox proportional hazards regression model as covariate rather than stratifying Cox analysis by gender. In addition site will also be included in the

Effective: 14-Feb-13

Page 23 of 26

model. The confidence intervals for the hazard rations will also be two-tailed rather than onetailed as specified within the protocol.

Reason: To ensure the modelling and presentation of confidence intervals is consistent with other multivariate statistical models specified within the statistical analysis plan.

1. INTRODUCTION

This document is an addendum to the statistical analysis plan dated 18th June 2014 for the analysis of the US WorldMeds, LLC study USWM-LX1-3003-1.

All decisions were taken prior to database lock.

2. CHANGES TO EXISTING ANALYSIS PLAN

Change 1

Section 6.1 General

Add following sentence

For all statistical models analyzed via log-transformed data the back-transformed LS means will be presented in the output.

Change 2

Section 6.2 Derived Data

Site Pooling for Statistical Analysis

The following text was removed:

For the purposes of statistical analyses models where site is included within the model as a fixed effect, sites randomizing < 6 subjects will be pooled from smallest to largest until the pooled site subsequently created has at least 6 subjects. In the event that the pooling of sites with less than 6 subjects does not result in a site with > 6 subjects, then that pooled site with < 6 subjects will also be pooled with the next largest site with > 6 subjects. To break ties if more than one site has the same number of subjects, the site identifier will be used as a secondary sort key.

Justification

The primary analysis no longer includes site in the model; therefore site has been removed as a variable from all subsequent statistical models.

Effective: 24-Dec-2014

Page 3 of 29

Change 3

Section 6.3 Analysis Populations

An additional population has been added

The **per-protocol population.** This analysis set will be a subset of the mITT population and will consist of all subjects who satisfy all of the inclusion/exclusion criteria and who correctly receive the treatment to which they are randomized and do not have a major protocol deviation within the double-blind phase. The selection of subjects for the per-protocol population will be made prior to database lock. Major protocol deviation will be broadly classified into five main categories based on ICH Harmonised Tripartite Guideline Structure and Content of Clinical Study Reports E3:

- 1. those patients who enter the study despite not satisfying entry criteria
- 2. those patients who developed non-safety related withdrawal criteria during the study and were not withdrawn
- 3. those patients who received the wrong treatment
- 4. those patients who received an excluded concomitant treatment, defined as any drug that is not included in the approved list of medications (as outlined in Appendix 16.2.2) or any antibiotic
- 5. lack of major compliance with the protocol.

The only variable to be assessed using the per-protocol analysis set will be the primary efficacy endpoint.

Justification

Due to the identification of some subjects taking prohibited medication during the double-blind period; a per-protocol population has been added to conduct a sensitivity analysis on the primary endpoint.

Effective: 24-Dec-2014

Page 4 of 29

Change 4

Section 6.7.2 Variables Considered

Medical History

Add the text in bold

Separate tabulations will be produced for previous and ongoing conditions with all conditions coded using MedDRA Version 16.0 (primary system organ class and preferred term). An ongoing condition is defined as any history with any of the following

- ≠ Marked as ongoing
- \neq With a missing stop date and ongoing not checked
- \neq Or a stop date after the first dose of study medication.

Justification

To make the definition clearer of what constitutes an ongoing condition.

Change 5

Section 6.7.2 Variables Considered

Infectious Disease Panel and Syphilis Tests at Screening

≠ HBsAg (Reactive, Non-reactive)

Amend to

≠ HBsAg (**Confirmed Positive**, Non-reactive)

Justification

Changed due to how the data is actually recorded on the laboratory vendor file.

Effective: 24-Dec-2014

Page 5 of 29

Change 6

Section 6.9 Primary Endpoint

Amend to

The primary efficacy endpoint is the difference between the overall LS means from a pattern mixture model based on log-transformed SOWS-Gossop scores from Days 1 through 7.

The study null hypothesis H₀ and alternative hypothesis H₁ are as follows:

 H_0 : There is no difference in the overall means in log-transformed SOWS-Gossop scores from Days 1 through 7 between either of the 2.4 mg lofexidine and 3.2 mg lofexidine doses and placebo.

 H_1 : There is a difference in the overall means in log-transformed SOWS-Gossop scores from Days 1 through 7 between either of the 2.4 mg lofexidine and 3.2 mg lofexidine doses and placebo.

The null hypothesis H_0 will be rejected in favor of H_1 if there is evidence at the $\alpha = 5\%$ significance level using a 2-sided test. Furthermore if H_0 is rejected in favor of H_1 and the overall LS mean is less for the lofexidine dose in comparison to placebo, then any lofexidine dose for which there is evidence of a difference will be declared superior to placebo in the treatment of opioid withdrawal in adult patients with opioid dependence. To account for multiplicity of statistical hypothesis testing of two lofexidine doses, statistical significance of the comparison of high dose lofexidine to placebo must be established, before significance of the comparison of low dose lofexidine to placebo can be claimed.

Justification

The primary efficacy endpoint has changed from the area under the curve (AUC) from Days 1 to 7 of the SOWS-Gossop scores to the overall (i.e., averaged over study Days 1 through 7) least squares (LS) means from a pattern mixture model based on log-transformed SOWS-Gossop scores from Days 1 through 7. The new endpoint stems from a revision of the pattern mixture model that incorporates comments on the modeling approach from the US Food and Drug Administration (FDA) in relation to patients who discontinue treatment.

Using the proposed pattern mixture model, the combined process of imputation followed by MMRM does not assume MAR and provides an unbiased estimate of the treatment effect that follows under the assumption that the mechanism by which data are missing not at random (MNAR) is that upon withdrawal from the study, the SOWS-Gossop trajectory of subjects randomized to lofexidine evolves as the trajectory of placebo subjects. Thus, by assigning an

Effective: 24-Dec-2014

Page 6 of 29

unfavorable placebo trajectory to patients who discontinue lofexidine treatment, the proposed model has addressed this concern. The nature of these changes is described in Change 7, following.

Change 7

Section 6.9.1 Principal Analysis

Amend to

A pattern-mixture approach⁵ will be used in assessing SOWS-Gossop from Days 1 to 7 inclusive using the mITT population.

It will be assumed that subjects randomized to lofexidine who withdraw from the study will have a time trajectory comparable to placebo post withdrawal. The pattern-mixture model will be implemented using multiple imputations (Ratitch⁶, 2011). The imputation of missing values and the analysis will be performed multiple times (20 imputed datasets) with the initial seed value set at '123', and the inference of this sensitivity analysis will be based on the combined estimates using the standard multiple imputation technique. This method is detailed in the section entitled "Pattern-Mixture Model with Control-Based Pattern Imputation" (Ratitch⁷, 2013). Briefly, the initial step is to impute the relatively rare, non-monotone missing data via the MCMC Option of SAS® PROC MI. This step uses iterative methods, with which non-convergence is a possibility; should an MCMC imputations that converge will be used in the analysis. This imputation model will be implemented for each combination of gender and treatment. (It should be noted that by performing the imputation for each such combination, the imputation modelling will be richer than the model used to inferentially analyse the data. It is acceptable, even preferable, for the imputation model to be richer than for the analysis model (see Little and Rubin, 2002).

The next step applies to the monotone missing data. The values for each pattern will be imputed using the chained equation method by SAS® PROC MI option MONOTONE REG. This MNAR imputation employs only the appropriate data for each pattern. That is, the missing data for lofexidine treatment arm at time t will be imputed using only the data on placebo subjects up to time t and the data for lofexidine subjects who have data up to time t-1 but are missing data at time t. The model for imputing missing data at time t will include fixed effect terms for study day from the baseline visit through to the t-1 visit and sex. Note that a term for treatment group is not included in this imputed data sets will be analyzed using the MMRM model described below and then summarized using PROC MIANALYZE. The model will include fixed effects for treatment group, baseline log_e (SOWS-Gossop score +1), sex, study day (days 1-7), and

Effective: 24-Dec-2014

Page 7 of 29

treatment group-by-day interaction. In this model the treatment group term in the model represents the effect of treatment over days 1 to 7. An unstructured covariance model will be used. However, in the event that this model does not converge then the following covariance models will be used in order until the model converges: Toeplitz, first-order autoregressive and compound symmetry. Analysis will be performed using PROC MIXED in SAS and the resultant F-tests will be based on Kenward-Roger's adjusted degrees of freedom.

Justification

Fitting an MMRM analysis without the imputation described above would have entailed an assumption that the missing data are missing at random (MAR). The combined process of imputation followed by MMRM does not assume MAR and provides an unbiased estimate of the treatment effect that follows under the assumption that the mechanism by which data are missing not at random (MNAR) is that upon withdrawal from the study, the SOWS-Gossop trajectory of subjects randomized to lofexidine evolves as the trajectory of placebo subjects.

Change 8

Section 6.9.1 Sensitivity Analysis

The text in bold has been edited:

The following sensitivity analyses will be conducted:

- \neq The above analysis will be performed using the per-protocol population.
- ≠ The log_e (SOWS-Gossop score plus 1) from day 1 to day 7 will be analyzed using a MMRM model on the mITT population.

The model will include fixed effects for treatment group, baseline log_e (SOWS-Gossop score plus 1), sex, study day (days 1-7) and treatment group-by-day interaction. In this model the treatment group term in the model represents the effect of treatment over days 1 to 7. An unstructured covariance model will be used. However, in the event that this model does not converge then the following covariance models will be used in order until the model converges: Toeplitz, first-order autoregressive and compound symmetry. Analysis will be performed using PROC MIXED in SAS and the resultant F-tests will be based on Kenward-Roger's adjusted degrees of freedom. This MMRM analysis assumes that the missing data are missing at random (MAR). This analysis provides an unbiased estimate of the treatment effect that would have been observed had all subjects continued

Effective: 24-Dec-2014

Page 8 of 29

on treatment until day 7. It therefore assumes that the response for withdrawn subjects would have followed the trajectory of the respective treatment after discontinuation, had they not withdrawn.

- In a further sensitivity analysis on the mITT population a "tipping point analysis" (Ratitch⁷, 2013) will be conducted in order to understand the "tipping point" δ at which the conclusions change from being statistically significant at the α =5% level using a 2sided test in favor of lofexidine to not statistically significant. This sensitivity analysis as per the sensitivity analysis described above begins with an imputation of the relatively rare non-monotone missing data using the MCMC option of PROC MI, based on standard MAR assumptions. The random seed for this set of analyses will be '456'. Then several analyses will be performed, indexed by the value δ , in each of which all monotone missing values are imputed using standard MAR assumptions, except in the imputation model in this instance will also include a covariate for **treatment.** In the first such analysis $\delta = 0$, which effectively is last observation carried forward. In general, δ is the adjustment that is added to the log_e (SOWS-Gossop score +1) at each visit after dropout during imputation. This increment is only added to the missing visits for the lofexidine groups. Delta is increased in increments of 1 (on the original SOWS-Gossop scale, before log transformation) until the point at which the comparison for the lofexidine group to placebo loses statistical significance. (An increment of 1 is selected, because the SOWS-Gossop scale ranges from its lowest to highest score by consecutive integers.) Effectively this analysis provides the amount by which the lofexidine subjects who discontinued early would need to be worse at each visit for the null hypothesis of no treatment difference to no longer be rejected. The imputed datasets are analyzed with the same MMRM model used in the primary analysis. The results are analyzed using PROC MIANALYZE.
- ≠ The studentized residuals will be assessed for normality using a histogram and quantilequantile plot. Other diagnostic tests may be performed following the inspection of data and potential outliers. If departures from normality or outliers are detected then nonparametric analysis may be conducted. Full details will be provided within the final SAP prior to database lock. These diagnostics will be performed for all ANCOVA and MMRM analyses specified within this SAP.

Justification

As a result of changes made to the principal statistical analysis (Change 7 annotated, Section 6.9.1) of the primary endpoint, the planed sensitivity analyses also required modification. Further, a per-protocol analysis of the primary endpoint was added due to the number of reported major protocol deviations.

Effective: 24-Dec-2014

Page 9 of 29

Change 9

Section 6.10 Secondary Endpoint

The following text was amended:

The secondary efficacy endpoint is the completion status (i.e., whether a subject receives at least one dose of study medication on Day 7 and completes the 3.5-hour post-dose SOWS-Gossop assessment on Day 7). The proportion of subjects in each treatment arm who receive at least one dose of study medication on Day 7 and complete the 3.5-hour post-dose SOWS-Gossop assessment on Day 7 will be analyzed using a logistic regression model including fixed effects for treatment group and gender using the mITT population. One test will compare the 3.2 mg lofexidine group to placebo; a second will compare the 2.4 mg Lofexidine group to placebo. A sensitivity analysis will be performed on this endpoint using the ITT population.

Justification

Site has been removed as a variable from all statistical models. All references for site will be removed from the statistical analysis plan where previously included in statistical models.

Change 10

Section 6.11 Tertiary/Exploratory Endpoints

Amend the following text related to SOWS-Gossop on Days 1, 2, 3, 4, 5, 6, and 7

An MMRM model will be used to test for a difference in the log_e (SOWS-Gossop score +1) at each of days 1, 2, 3, 4, 5, 6, and 7 between the 3.2 mg Lofexidine group and placebo and between the 2.4 mg Lofexidine group and placebo. The model will include fixed effects for treatment group, baseline log_e (SOWS-Gossop score +1), sex, visit (day 1, day 2, day 3, day 4, day 5, day 6 and day 7) and treatment-by-visit interaction. An unstructured covariance model will be used. However, in the event that this model does not converge then the following covariance matrix will be used in order until the model converges: Toeplitz, first-order autoregressive and compound symmetry. Analysis will be performed using PROC MIXED in SAS and the resultant F-tests will be based on Kenward-Roger's adjusted degrees of freedom.

Effective: 24-Dec-2014

Page 10 of 29

Justification

The primary analysis no longer includes site in the model; therefore site has been removed as a variable from all subsequent statistical models.

Change 11

Section 6.11 Tertiary/Exploratory Endpoints

Amend the following text related to OOWS-Handelsman, MCGI (Subject and Rater), VAS-E, and COWS

The same methods used for SOWS-Gossop detailed above on days 1, 2, 3, 4, 5, 6, and 7 will be used for OOWS-Handelsman, MCGI (Subject and Rater), VAS-E, and COWS scores on days 1, 2, 3, 4, 5, 6, and 7. Depending on the distribution of these outcomes data transformations maybe used to normalise the data. Any transformation will be specified within the SAP prior to database lock.

The text in bold was added to the following:

The same methods used for SOWS-Gossop detailed above on days 1, 2, 3, 4, 5, 6, and 7 will be used for OOWS-Handelsman, MCGI (Subject [Severity of opiate withdrawal and side effect index separately] and Rater [Severity of illness and side effect index separately], VAS-E, and COWS scores on days 1, 2, 3, 4, 5, 6, and 7, where the baseline covariate will be the baseline value of the endpoint under analysis. The same model will be used for MCGI [Subject and Rater] and VAS-E, except that there will be no baseline covariate as these endpoints do not have a baseline measurement. Depending on the distribution of these outcomes data transformations maybe used to normalise the data. Any transformation will be specified within the SAP prior to database lock.

Justification

